2.5 Analysis supporting primary objective

The primary objective is to determine whether prophylactic dapagliflozin plus metformin XR compared to prophylactic metformin XR alone reduces the occurrence of severe hyperglycemia events over the first eight weeks of alpelisib plus fulvestrant treatment (from Cycle 1 Day 8 to Cycle 3 Day 8).

2.5.1 Primary endpoint

The primary endpoint (variable attribute of the primary estimand; refer to [Section 1.2.1](#)) is the occurrence of severe (Grade ≥ 3) hyperglycemia over the first eight weeks of alpelisib plus fulvestrant treatment, defined as any glucose laboratory values > 250 mg/dL (> 13.9 mmol/L) from Cycle 1 Day 8 to Cycle 3 Day 8.

Note: assessments from Cycle 1 Day 5 up to Cycle 3 Day 11 are allowed due to the 3-day visit window (Protocol Section 8).

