### Figure 3-1 Study Design

**Figure 3-2** Study Flow Chart

The primary endpoint is the occurrence of severe (Grade  $\geq 3$ ) hyperglycemia events (based on glucose laboratory values) over the first eight weeks of alpelisib plus fulvestrant (from Cycle 1 Day 8 to Cycle 3 Day 8) with prophylactic treatment with dapagliflozin plus metformin XR compared to alpelisib plus fulvestrant with prophylactic metformin XR in participants who have at least one baseline risk factor associated with severe hyperglycemia.

The study will consist of 4 phases: molecular pre-screening, screening (28 days), randomized treatment, and post-treatment follow-up (safety follow-up and efficacy follow-up if applicable) as described in the study flow chart ([Figure 3-2](#)).

Treatment with fulvestrant and dapagliflozin plus metformin XR or metformin XR will be initiated on Cycle 1 Day 1 and be administered continuously. Alpelisib treatment begins one

week after the start of antihyperglycemic therapy (Cycle 1 Day 8) to allow for initial titration prior to alpelisib dosing.

The duration of treatment with alpelisib and fulvestrant will be 12 cycles or until disease progression, unacceptable toxicity, or discontinuation from study treatment for any other reason, whichever comes first. A cycle of treatment is defined as 28 days.

After treatment discontinuation, all participants will enter the safety follow-up which will end 30 days after participant discontinues from study treatment.

Participants who discontinue for reasons other than disease progression, death, lost to follow-up, or withdrawal of consent/opposition to use of data/biological samples before completing 12 cycles of treatment will additionally enter post-treatment efficacy follow-up. Post-treatment efficacy follow-up will end 12 cycles after randomization.

After the 12 cycles treatment period for alpelisib plus fulvestrant, participants who, in the opinion of the Investigator, are benefiting from study treatment may switch to commercially available supply.

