## 6.3.2 Instruction for prescribing and taking study treatment

### 6.3.2.1 Alpelisib administration

Alpelisib 300 mg is taken orally once daily on a continuous dosing schedule starting on Cycle 1 Day 8 under fed conditions. Dose reductions to 250 mg and 200 mg will be permitted (see [Section 6.6.1.1](#)). If further dose reductions are indicated, the participant will be permanently discontinued from alpelisib.

The Investigator or responsible site personnel should instruct the participant to take the study drugs as per protocol (promote compliance). Drug accountability must be performed on a regular basis. Participants will be instructed to return unused alpelisib tablets to the site at the end of each cycle or at the time of discontinuation of study treatment. The site personnel will ensure that the appropriate dose of each study drug is administered at each visit and will provide the participant with the correct amount of drugs for subsequent dosing.

Alpelisib is dosed on a flat scale of mg/day and not by weight or BSA. There will be no breaks between dosing cycles. Participants should be instructed to take the dose of alpelisib at approximately the same time each day immediately after food (preferably in the morning), except on the days blood collection is scheduled at the clinic, at which time the participants should take their doses at the clinic at any later point of time.

Alpelisib tablets should be swallowed whole (tablets should not be chewed, crushed or split prior to swallowing). Tablets that are broken, cracked, or otherwise not intact should not be ingested.

On the days of fulvestrant administration, alpelisib tablets should be taken 1 hour prior to the infusion of fulvestrant.

Should any participant enrolled on the study miss a scheduled dose of alpelisib, the participant will be allowed to take immediately the missed scheduled dose up to a maximum of 9 hours after that scheduled dose time. If greater than 9 hours after the scheduled dose time, the missed dose should not be taken, and the participant should take their allotted dose at the next scheduled time.

If the participant vomits after taking the alpelisib dose, the participant should not take an additional dose on that day and should resume the usual dosing schedule the next day at the usual time.

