**Table 8-1      Allowable visit windows**

Visit name	Window
Screening	-28 to -1 or -14 to -1 days as detailed in Table 8-2
Fulvestrant injection	Cycle 1 Day 1 and Cycle 1 Day 15 (if applicable) and on Day 1 ± 3 days of every subsequent cycle
Tumor assessments	± 7 days
All other assessments during the treatment period	± 3 days
Safety follow-up	± 3 days
Efficacy follow-up	± 7 days
End of Treatment (EOT)	≤ 14 days after permanent discontinuation of study treatments

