**Table 8-2 Assessment Schedule**

Period	Pre-screening	Screening		Cycle 1				Cycle 2				Cycle 3		Cycle 4 to 12	EOT	Post-Treatment follow-up	
Visit Name	Molecular Pre-screening	Screening		C1D1	C1D8	C1D15	C1D22	C2D1	C2D8	C2D15	C2D22	C3D1	C3D8	C4D1 to C12D1	EOT	Safety follow-up	Efficacy follow-up (if applicable)
Days	-	-28 to -1	-14 to -1	1	8	15	22	1	8	15	22	1	8	1	14 days after last dose	30 days after last dose	see section 8.3
Medical history/current medical conditions		X															
Diagnosis and Extent of Cancer		X															
ER/PgR status		X															
HER2 status		X															
Prior antineoplastic therapies		X															
Prior or concomitant non-drug therapies/procedures		X		Continuous up to 30 days after last dose of study treatment													
Prior/concomitant medications		X		Continuous up to 30 days after last dose of study treatment													
Performance status (ECOG)			X					X				X		X	X		
Body Height			X														
Body Weight			X					X				X		C4D1 then as clinically indicated	X		
Abdominal Girth			X									X			X		

Period	Pre-screening	Screening		Cycle 1				Cycle 2				Cycle 3		Cycle 4 to 12	EOT	Post-Treatment follow-up	
Visit Name	Molecular Pre-screening	Screening		C1D1	C1D8	C1D15	C1D22	C2D1	C2D8	C2D15	C2D22	C3D1	C3D8	C4D1 to C12D1	EOT	Safety follow-up	Efficacy follow-up (if applicable)
Days	-	-28 to -1	-14 to -1	1	8	15	22	1	8	15	22	1	8	1	14 days after last dose	30 days after last dose	see section 8.3
Physical Examination		S		S	S			S		S		S		S	S		
Vital Signs		X	X		X			X		X		X		X	X		
Hematology		X			X			X		X		X		X	X		
Fasting Chemistry (Full)			X					X				X		X	X		
Fasting Chemistry (Partial) 					X					X							
Fasting Plasma Glucose 			X	X	X	X	X	X	X	X	X	X	X	X	X		
Ketones			X	X		X		X		X		X		X	X		
HbA1c			X					X				X		C5D1 + C8D1 + C11D1	X		
Fasting Insulin level			X	X	X	X	X	X	X	X	X	X	X	X	X		
Fasting Lipid Panel			X													X	
Coagulation			X	As clinically indicated											X		
Fasting Lipase, Fasting Amylase			X					X				X		X	X		
Urinalysis (Macroscopic) 			X	As clinically indicated											X		
Tumor Assessment		X		Every 8 weeks until disease progression, death, loss to follow-up, withdrawal of consent/oppose the use of their data											X		Every 8 weeks until disease

Period	Pre-screening	Screening		Cycle 1				Cycle 2				Cycle 3		Cycle 4 to 12	EOT	Post-Treatment follow-up	

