#### **8.4.1 Laboratory evaluations**

Clinical laboratory analyses are to be performed by the central laboratory.

Safety samples that can be collected remotely will be collected and analyzed in line with the study laboratory manual. Where samples are collected and analyzed at a local laboratory instead of the central laboratory, Novartis will ensure the results reported are equivalent to central laboratory collection and analysis.

In case of urgent safety management of hyperglycemia, fasting plasma glucose assessment can be done locally according to the schedule of assessments and collection plan outlined respectively in [Table 8-2](#) and [Table 8-6](#).

Unscheduled local laboratory assessments may be performed if medically indicated to assess a (potential) adverse event or when the treating physician cannot wait for central laboratory results for decision making (e.g., dose modifications). In this particular situation, if possible, the blood sample obtained at the same time point should be submitted to the central laboratory for analysis in parallel with local analysis.

As per [Section 4.6](#), during a Public Health emergency as declared by Local or Regional authorities, i.e. pandemic, epidemic or natural disaster, that limits or prevents on-site study visits, if participants cannot visit the site for protocol specified safety laboratory assessments, an alternative laboratory (local) collection site may be used.

The results of the local laboratory will be recorded in the eCRF if any of the following criteria are met:

- A treatment decision was made based on the local results, or
- Local laboratory results document an adverse event not reported by the central lab, or
- Local laboratory results document an adverse event severity that is worse than the one reported by the central lab, or
- There are no concomitant central results available

**For assessment of participants' eligibility for the study, only laboratory results from the central laboratory will be used with the exception of the following where local laboratory results are acceptable:**

- **Postmenopausal status (FSH and estradiol) if applicable and**
- **PIK3CA mutational status (if done locally using FDA-approved PIK3CA CDx test for alpelisib or the CE-IVD QIAGEN therascreen PIK3CA RGQ PCR test)**

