2.5.2 Statistical hypothesis, model, and method of analysis

The primary analysis to assess the difference in the percentage of participants with severe hyperglycemia between the two treatment arms will not be conducted.

The occurrence of severe hyperglycemia from Cycle 1 Day 8 to Cycle 3 Day 8 documented after the initiation of additional antihyperglycemic therapies will be counted for the primary endpoint summary (refer to [Section 1.2.1](#) for more information on primary estimand).

The primary endpoint will be summarized based on the Safety Set according to the treatment participants actually received. The percentage of participants with severe hyperglycemia per treatment arm will be summarized without confidence intervals.

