2.7.4 Laboratory data

Regarding laboratory assessments, data from all sources (central and local laboratories) will be combined. Listing of participants with CTC grade 3 or 4 laboratory abnormalities will be provided.

Liver function parameters

Liver function parameters of interest in this study are total bilirubin (TBIL), ALT, AST and alkaline phosphatase (ALP).

The participants meeting the following categorical liver function test criteria will be listed:

- ALT > 3xULN, 5xULN, 10xULN, 20xULN
- AST > 3xULN, 5xULN, 10xULN, 20xULN
- ALP > 1.5xULN
- ALT or AST > 3xULN, 5xULN, 8xULN, 10xULN, 20xULN
- TBIL > 2xULN, 3xULN

For the following combined categories (the assessments need not be concurrent, i.e. participants are counted based on their most extreme value for each parameter. Further medical review can assess potential confounding factors such as, liver metastases, liver function at baseline etc.

- If AST and ALT \leq ULN at baseline
 - ALT or AST > 3x ULN & TBIL > 2x ULN
 - ALT or AST > 3x ULN & TBIL > 2x ULN & ALP \geq 2x ULN
 - ALT or AST > 3x ULN & TBIL > 2x ULN & ALP < 2x ULN
- If AST and ALT > ULN at baseline
 - Elevated ALT or AST (> 3x Baseline value or 8x ULN) & TBIL (> 2x Baseline value and 2x ULN)
 - Elevated ALT or AST (> 3x Baseline value or 8x ULN) & TBIL (> 2x Baseline value and 2x ULN) & ALP \geq 2x ULN
 - Elevated ALT or AST (> 3x Baseline value or 8x ULN) & TBIL (> 2x Baseline value and 2x ULN) & ALP < 2x ULN

Additional categories may be added to the above list based on any updates to the internal guidelines on collection, analysis, and presentation of liver safety data.

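### The SAP's primary-endpoint note opens the count at Cycle 1 Day 5, inside the planned alpelisib-free week, without requiring that alpelisib has started

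*SAP*

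**What the plan says.** SAP 2.5.1 and Protocol 12.4.1 define the event alike: severe hyperglycemia in the first eight weeks on alpelisib plus fulvestrant, meaning a glucose result above 250 mg/dL (13.9 mmol/L) from C1D8 to C3D8. The SAP alone adds a note: "assessments from Cycle 1 Day 5 up to Cycle 3 Day 11 are allowed due to the 3-day visit window". The tolerance comes from Protocol Table 8-1, where the row "All other assessments during the treatment period" carries ±3 days.

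On dosing, Protocol 6.3.2.1 says: "Alpelisib 300 mg is taken orally once daily on a continuous dosing schedule starting on Cycle 1 Day 8 under fed conditions". Protocol Section 3 gives the reason for the delay: alpelisib begins one "week after the start of antihyperglycemic therapy (Cycle 1 Day 8) to allow for initial titration prior to alpelisib dosing".

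On which glucose values exist, the "Fasting Plasma Glucose" row of Protocol Table 8-2 has draws at C1D1 and C1D8 and none between. Protocol 8.4.1 adds: "Unscheduled local laboratory assessments may be performed if medically indicated to assess a (potential) adverse event". SAP 2.7.4 states that "data from all sources (central and local laboratories) will be combined".

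SAP 2.5.2, on counting events after extra glucose-lowering treatment, keeps the nominal days: "The occurrence of severe hyperglycemia from Cycle 1 Day 8 to Cycle 3 Day 8 documented after the initiation of additional antihyperglycemic therapies". The formal primary analysis is cancelled. What remains is the percentage per arm, without confidence intervals.

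**The concern.** A visit tolerance and a counting window do different jobs. The first says when a scheduled visit may take place. The second says which results are events. The note uses the first as the second, and since the endpoint accepts any glucose result above the threshold, the widened window is not confined to results from a displaced C1D8 visit.

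No other SAP rule closes the gap for a participant who is later dosed. The treatment-policy rules in SAP 2.5.3 deal with values after alpelisib is stopped, interrupted or reduced, after the prophylactic agents are stopped or interrupted, or where alpelisib was never given. None describes a value before a planned first dose. Baseline in SAP 2.1.1.8 is tied to the first dose of any component, normally on Day 1, so a Day 5 to 7 value is already post-baseline.

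At stake is whether the one primary-endpoint figure still to be reported measures what its label says. A literal programmer would count a Day 6 value in a participant dosed on Day 8. Another, relying on the endpoint's title, would not.

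**Working it through.** **Inputs.** Cycle length 28 days (Protocol Section 3); nominal window C1D8 to C3D8 (Protocol 12.4.1, SAP 2.5.1); note window C1D5 to C3D11 (SAP 2.5.1); planned alpelisib start C1D8 (Protocol 6.3.2.1); planned 66 participants per arm (Protocol Section 3).

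**The plan's own figure.** Study day = (cycle − 1) × 28 + day. C1D8 is Day 8 and C3D8 is 56 + 8 = Day 64. The difference is 56 days, or eight weeks, so the stated period is reproduced.

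**The two windows, counted inclusively.**
- Nominal: 64 − 8 + 1 = 57 days.
- Note: C1D5 is Day 5 and C3D11 is 56 + 11 = Day 67, so 67 − 5 + 1 = 63 days.

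**Calendar days before alpelisib that fall inside the window, for first-dose day s.** Note: s − 5. Nominal: max(0, s − 8). With the fix below, the count opens at min(s, 8), again leaving max(0, s − 8).

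| First alpelisib day | Note | Nominal | Added by note | After fix |
|---|---|---|---|---|
| 5 | 0 | 0 | 0 | 0 |
| 8 (as planned) | 3 | 0 | 3 | 0 |
| 11 | 6 | 3 | 3 | 3 |

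For a planned start the note admits 3 pre-alpelisib days, 3/63 = 4.8% of its window.

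**The SAP's own dates.** The example in SAP 2.1.1.4 has fulvestrant on 01-Jan-2022 and alpelisib on 08-Jan-2022. Taking 01-Jan as C1D1, the note opens on 05-Jan, so 5, 6 and 7 January are countable before alpelisib.

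**Scheduled data in the added days.** No fasting glucose draw is scheduled on Days 2 to 7. At nominal timing, Days 5 to 7 therefore hold no scheduled draw, and a value can arise only from an unscheduled test or a C1D8 visit held early.

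**Size of one misclassification.** One participant counted for such a value, with no later qualifying value, moves the arm's percentage by 100/n. At the planned 66 that is 100/66 = 1.5 points. The number actually enrolled before recruitment stopped is not given. If it were 10 to 30 per arm (an assumption), the shift would be 100/10 = 10 to 100/30 = 3.3 points.

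**The case against.** The strongest reply is that the note states its own purpose. It cites the visit window, so its natural use is to keep a C1D8 or C3D8 visit held a few days early or late. Protocol 6.3.2.1.1 has study treatment taken in the clinic on scheduled visit days, so an early C1D8 visit may well carry the first dose. The Day 5 opening would then rescue on-drug values that a fixed Day 8 opening would lose. This stands. It makes an early draw with dosing left to Day 8 less likely, and it is why the fix should not simply delete the early opening. It does not cover an unscheduled Day 5 to 7 value in a participant dosed on Day 8, which the wording admits.

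A second reply is that a pre-dose value is already part of the protocol's endpoint. The window opens at C1D8, and Protocol 6.7.2 places the fasting sample before breakfast and alpelisib. This also stands. A reader might infer that every pre-alpelisib value contradicts the endpoint and that counting should start strictly at the first dose. The documents do not support that: the C1D8 sample lies inside the protocol's definition, and SAP 2.5.3 deliberately counts values in participants never given alpelisib. A strict first-dose anchor would drop a scheduled sample and would treat late starters differently from never-dosed participants on Days 8 to 10, when both are off the drug.

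A third reply is that SAP 2.5.2 repeats the nominal days as shorthand, the tolerance having been set once in 2.5.1. That is a fair reading. The two sections should be aligned, but the difference need not be a contradiction.

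**Conclusion.** The point holds as a minor defect in the endpoint definition. As worded, SAP 2.5.1 can score an unscheduled glucose value above 250 mg/dL on Days 5 to 7 as an on-alpelisib event in a participant first dosed on Day 8, outside the window in Protocol 12.4.1.

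The effect is probably very small. At most 3 pre-alpelisib days are added, with no scheduled draw in them at nominal timing. Exclusion criterion 14 removes type II diabetes with fasting plasma glucose above 160 mg/dL or HbA1c above 8%, so values above 250 mg/dL before alpelisib should be few. The documents give no rate for them, so this is a judgment. The 4.8% is a share of calendar time and does not estimate an error rate.

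A reader might infer that the note biases the comparison between arms or undermines the trial's conclusion. The documents do not support that. The rule is the same in both arms, no test or confidence interval remains, and Grade 3 and 4 laboratory values will be listed under SAP 2.7.4, so an affected participant would be visible.

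**What to change.** In SAP 2.5.1, replace the lower limit in the note with one rule: counting opens at C1D8, or at the first alpelisib administration date (already derived under SAP 2.1.1.2) if that date falls on Days 5 to 7, and values dated on or after the opening day count. Participants never given alpelisib, and those who start after Day 8, keep the nominal C1D8 opening.

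Leave the rest alone: the end at C3D8 plus 3 days, the scheduled fasting sample at the visit of first dosing, and the treatment-policy rules. In SAP 2.5.2, refer to the limits in 2.5.1 instead of restating nominal days.

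The cost is one sentence in 2.5.1 and a cross-reference in 2.5.2, with no new data. There are two downsides. For early starters only, the opening day depends on the actual first-dose date. And if a C1D8 sample were drawn early with dosing left to Day 8, it would no longer count; the supervised-dosing instruction makes that case unlikely.

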2.5.2 Statistical hypothesis, model, and method of analysis

The primary analysis to assess the difference in the percentage of participants with severe hyperglycemia between the two treatment arms will not be conducted.

The occurrence of severe hyperglycemia from Cycle 1 Day 8 to Cycle 3 Day 8 documented after the initiation of additional antihyperglycemic therapies will be counted for the primary endpoint summary (refer to [Section 1.2.1](#) for more information on primary estimand).

The primary endpoint will be summarized based on the Safety Set according to the treatment participants actually received. The percentage of participants with severe hyperglycemia per treatment arm will be summarized without confidence intervals.

2.5.3 Handling of intercurrent events

The primary estimand will account for different intercurrent events as explained in the following:

- 1. Discontinuation of alpelisib or not receiving any alpelisib:** occurrence of severe hyperglycemia events collected after discontinuation of alpelisib or without any exposure to alpelisib will be used for the primary endpoint summary (treatment policy strategy)
- 2. Discontinuation and/or interruption of prophylactic antihyperglycemic therapies:** occurrence of severe hyperglycemia events collected after discontinuation and/or interruption of prophylactic antihyperglycemic therapies will be used for the primary endpoint summary (treatment policy strategy)

3. **Dose interruption and/or reduction of alpelisib:** occurrence of severe hyperglycemia events collected after dose interruption and/or reduction of alpelisib will be used for the primary endpoint summary (treatment policy strategy)

2.5.4 Handling of missing values not related to intercurrent event

Missing data will not be imputed.

2.5.5 Sensitivity analyses

Not applicable.

2.5.6 Supplementary analyses

Not applicable.

2.6 Analysis supporting secondary objectives

The secondary objectives are to compare the two treatment groups with respect to PFS, and to evaluate the overall response rate (ORR) and clinical benefit rate (CBR). The analyses will be based on FAS and will include all data observed up-to the cut-off date.

No inferential testing is planned for secondary endpoints.

2.6.1 Secondary endpoints

2.6.1.1 Progression-free survival (PFS)

PFS will not be analyzed due to the permanent halt of recruitment and early termination of study.

Overall response rate (ORR)

ORR with confirmed response is defined as the proportion of participants with BOR of confirmed complete response (CR) or confirmed partial response (PR), as per local review and according to RECIST 1.1 (see Section 16.4 of the study protocol) and [Section 5.4.2](#) of this document.

ORR with confirmed response will be calculated based on the FAS. Participants with only non-measurable disease at baseline will be included in the numerator if they achieve a complete response. Only tumor assessments performed before the start of any further anti-neoplastic therapies (i.e. any additional anti-neoplastic therapy or surgery) and within 30 days after the last administration of study treatment will be considered in the assessment of best overall response.

Further anti-neoplastic therapies will be identified from the data collected on the “Concomitant Antineoplastic Therapy” eCRFs with indication “Breast Cancer”. Palliative radiotherapy is the only setting of radiotherapy allowed during the study. Therefore, palliative radiotherapy will not be considered as an anti-neoplastic therapy for assessment of BOR. Continuation of combination partner therapy alone after end of study treatment will also not be considered as a new anti-neoplastic therapy.

Clinical benefit rate (CBR)

CBR with confirmed response is defined as the proportion of participants with a best overall response of confirmed complete response (CR) or confirmed partial response (PR), or an overall response of stable disease (SD) lasting for at least 24 weeks. CR, PR, and SD are defined as per local review according to RECIST 1.1 (see Section 16.4 of the study protocol). A participant will be considered to have SD for 24 weeks or longer if a SD response is recorded at 24-1=23 weeks or later from randomization, allowing for the ± 1 week visit window for tumor assessments. Participants with only non-measurable disease at baseline will be included in the numerator only if they achieve a complete response or have a 'Non-CR/Non-PD' response at 24-1=23 weeks or later from randomization.

ECOG performance status

The ECOG PS scale ([Table 2-3](#)) will be used to assess physical health of participants, ranging from 0 (most active) to 5 (least active):

Table 2-3 ECOG Performance Scale

Score	Description
0	Fully active, able to carry on all pre-disease performance without restriction
1	Restricted in physically strenuous activity but ambulatory and able to carry out work of a light or sedentary nature, e.g., light house work, office work
2	Ambulatory and capable of all self-care but unable to carry out any work activities. Up and about more than 50% of waking hours
3	Capable of only limited self-care, confined to bed or chair more than 50% of waking hours
4	Completely disabled. Cannot carry on any self-care. Totally confined to bed or chair
5	Dead

The intervals in [Table 2-4](#) will be used to group the ECOG PS data over time. Day in columns 2 and 3 is defined as date of ECOG PS assessment date – randomization date + 1. The correspondence with Day in column 1 assumes that a participant is treated on the day of randomization; however the definition of Day in columns 2 and 3 still applies if this is not the case, i.e. randomization date is taken as the reference for the windows.

Table 2-4 Time windows for ECOG PS assessments

Assessment	Target day of assessment	Time Interval
Baseline		\leq Day 1
Cycle 2 Day 1	29	Day 2 to day 42
Cycle 3 Day 1	57	Day 43 to day 70
Cycle 4 Day 1	85	Day 71 to day 98
Cycle k Day 1 ($k \geq 5$)	$d = (k-1) * 28 + 1$	Day $d-14$ to day $d+13$
End of Treatment		Assessment taken at the end of treatment visit

If more than one assessment is done within the same time window, the assessment performed closest to the target date will be used. If 2 assessments within a time window are equidistant from the target date, then the worst of the 2 assessments will be used.

